Although the text-Web intervention will be designed to be accessed over a continuous 5-day period; participants will be given a three-week window to access all intervention content, to allow for self-directed completion of the text-Web intervention. As soon as participants access all intervention content, the second health educator will be triggered to complete a post-intervention assessment. The post-assessment will be offered to participants over the phone or through an electronic link to the survey.

We will not provide participants equipment or electronic devices. The goal of this project is to assess whether a text-Web intervention is feasible and effective in real life circumstances, thus, with the participants' own devices. We will not pay for any data usage charges to participants. However, because we are compensating participants for study participation, they can use some of the money from study compensation to cover any data usage costs incurred. There are no limitations on what devices can be used. Though participants will have to either receive initial text messages either through a mobile phone or through a private Facebook message. A third option could be through an email address. Participants will then need to be able to access Web content, but they can do that at any place of their choosing: a mobile phone, a home computer, a public library computer, or at some other place.

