Standard of care discharge planning session (control arm). In the Aim 1 pilot study, participants will only access the intervention arm content. In the Aim 2 RCT, participants will be randomized after consent to the intervention or control arm. The women will be offered a 10-page women's health booklet that utilizes SHE-Women content, but in print form. The booklet will provide simple definitions, screening guidelines, and local health resources for age and risk appropriate cervical, breast cancer, unintended pregnancy, and STI prevention. We will collect multiple points of contact information for the participants: phone numbers, addresses for themselves or family members; usual places of hangout; and Facebook handle, for follow-up. Participants in this arm of the intervention will be contacted 5 days after receiving the standard of care intervention for post-assessment. Similar to the intervention arm, we expect to lose 30% of women to follow-up, thus we will over-recruit by about 30% for the RCT, as described above. Participants will be asked to reach out to us 5 days after or we will contact them for follow-up and to complete the post-assessment over the phone or through an electronic link to the survey.

We wish to note that although we call the control arm the "standard of care," in reality there is no standard discharge planning session in the jails we work with; women are sent out the door with their belongings. But we feel it would be grossly unethical to not provide the control arm with some health information, even if limited.

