Aim 1 pilot and Aim 2 RCT effectiveness outcomes data will be collected in surveys at baseline and post-intervention for Aim 1, and then also at 1, 2, and 3 years for Aim 2. For Aim 1, depending on the method of re-consenting original SHE participants (over the phone or in person), study staff will conduct the baseline assessment either over the phone or in person using a Web link on the SHE-Women study Website. The Web link to the survey will utilize audio computer-assisted self-interview (ACASI) technology, where the computer device will read the questions and answer options aloud as participants move through the assessment. Study staff will make themselves available in person or by phone to guide participants through the Web survey, if they desire this service. Participants will have the option to turn off audio if they cannot gain access to headphones or are in a public place. To facilitate use of ACASI, participants will be offered free headphones at study start, and then at quarterly check-ins, or follow-up surveys. We have used ACASI with other hard to reach low literacy populations with success (active drug users and with women leaving corrections in other cities). For the Aim 2 RCT, study staff will conduct the baseline assessment using the same Web link to the SHE-Women study Website so that participants become accustomed to survey administration using a secure Web link. Participants randomized to the control arm will not have access to any intervention content on the Website. All other surveys – post-intervention, and 1-, 2-, and 3-year follow-up surveys, will be administered using the same Web link to an ACASI-administered survey. Participants will always be given the option of completing the survey over the phone or in person with a member of the study staff, if that is their preference. If participants become re-incarcerated during the longitudinal follow-up, we can conduct surveys in person or through the mail with paper and pencil copies of the survey – we have previously employed these techniques.

Aim 3 perceptions and uptake data will be collected using the same methods described above for Aim 1.

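### The immediate knowledge test can be self-completed online with no rule closing the website content, so intervention women may find answers more easily than controls

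*Combined protocol and SAP*

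**What the plan says.** The relevant statements in the combined protocol and SAP are spread over several sections.

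- **Survey mode.** For the intervention arm (Intervention arms and procedures): "The post-assessment will be offered to participants over the phone or through an electronic link to the survey". Controls have the same choice, to "complete the post-assessment over the phone or through an electronic link to the survey" (Standard of care discharge planning session). Data collection adds that the post-intervention and annual surveys "will be administered using the same Web link to an ACASI-administered survey".
- **Supervision.** It is optional. Data collection describes staff help for the Aim 1 survey as follows: "Study staff will make themselves available in person or by phone to guide participants through the Web survey, if they desire this service". It then says of the follow-up surveys: "Participants will always be given the option of completing the survey over the phone or in person with a member of the study staff".
- **Timing, intervention arm.** "participants will be given a three-week window to access all intervention content", and "As soon as participants access all intervention content, the second health educator will be triggered to complete a post-intervention assessment". The Day 5 message also carries the invitation to the post-assessment.
- **Timing, control arm.** Controls are contacted 5 days after receiving their materials.
- **Website content.** Data collection: "Participants randomized to the control arm will not have access to any intervention content on the Website".
- **Print content.** Every woman is sent a booklet carrying the programme's material. The control-arm section describes a 10-page print version.
- **Outcome.** Table 5 lists knowledge scales for Pap, breast, contraception and STDs, alongside belief, self-efficacy and confidence measures. Validation strategies names health literacy among the primary outcomes.

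No text says that the content is closed before or during the survey, and none says that it stays open. No closed-book instruction appears for either arm.

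**The concern.** Knowledge items have factual answers. A woman in the intervention arm who opens the survey link on her own device, soon after the last module and within her access window, may be able to return to the teaching material while she answers. A control using the same link cannot reach that material on the site. If some women do this, part of the arm difference in knowledge at the immediate post-test reflects consulting the source, not learning.

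The direction favours the intervention. The mixed model in Data analysis compares change between arms and contains nothing that distinguishes look-up from learning. Literacy has only two post-baseline measurements (immediate and 1 year), so the immediate score carries much of the comparison. Knowledge also enters the screening and risk-reduction models as a covariate, so any inflation could carry over if the post-test score is the one used.

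**Working it through.** **1. Is differential look-up possible under the plan as written?** Unsupervised completion by link is allowed in both arms. The intervention-arm survey is triggered when content is finished, which for a woman on schedule is Day 5 of a 21-day window. Only controls are barred from the Website content. No lock or closed-book rule is stated. So it is possible. That the content is actually reachable during the survey is an inference from the window and the absence of a lock.

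**2. Reproduce the plan's power figure.** Inputs from Power: f = 0.12 (the stated conservative choice), t = 3, r = 0.46, N = 124, claimed power 80% for literacy. Alpha is 0.05 (Data analysis). For the repeated-measures group-by-time interaction with two arms:

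- λ = f² × N × t / (1 − r) = 0.0144 × 124 × 3 / 0.54 = 9.92
- df1 = (2 − 1)(3 − 1) = 2; df2 = (124 − 2)(3 − 1) = 244
- Power = 80.7%, which matches the stated 80%.

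The calculation sentence itself prints f = 0.13, which gives 86.9% and does not match. I therefore use f = 0.12.

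**3. Convert f to an arm difference in SD.** Put a shift d in one cell of the 2 × 3 table (intervention arm, post-test). The interaction residuals are ±d/3 in the two post-test cells and ±d/6 in the other four. Then

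- f² = [2(d/3)² + 4(d/6)²] / 6 = d²/18, so f = d/√18
- f = 0.12 corresponds to d = 0.12 × √18 = 0.51 SD. (At f = 0.13 it would be 0.55 SD.)

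**4. Size of a look-up shift (assumed).** The documents give no look-up rate or gain. Let a share u of intervention women look up answers, each gaining g SD, with none among controls. Then d = u × g.

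- u = 10%, g = 1: d = 0.10 SD. The same d arises from u = 20%, g = 0.5.
- u = 20%, g = 1: d = 0.20 SD. The same d arises from u = 40%, g = 0.5.
- Relative to the design effect: 0.10/0.51 ≈ 20%; 0.20/0.51 ≈ 39%.

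**5. False-positive rate of the interaction test on a knowledge scale, with no true effect** (N = 124, r = 0.46, shift at the post-test only):

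| Shift d (SD) | f = d/√18 | λ | Rejection rate |
|---|---|---|---|
| 0 | 0 | 0 | 5% |
| 0.05 | 0.012 | 0.10 | 5.7% |
| 0.10 | 0.024 | 0.38 | 8.0% |
| 0.20 | 0.047 | 1.53 | 17.9% |

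If controls look up half as often, from the booklet, each shift halves: 0.10 becomes 0.05 (5.7%) and 0.20 becomes 0.10 (8.0%). With 200 women analysed, shifts of 0.10 and 0.20 SD give 9.9% and 26.9%, because a fixed bias weighs more as precision improves.

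**6. Wider range.** With u from 10% to 50% and g from 0.5 to 1, at N = 124 and no look-up by controls, the rate runs from 5.7% to 79.2%. Reproducing the whole design effect by look-up alone would need about 51% of the arm to gain 1 SD each.

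**The case against.** The strongest reply is that much of this is silence in the document, and that controls are not cut off from answers. Several parts of it stand.

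- **Continued access is not documented.** A reader might infer that the content is open during the survey. The protocol does not say so. The supportable statement is that nothing closes it.
- **Look-up is not confined to one arm.** A reader might infer that controls have nothing to consult. They have the printed booklet, may text a health educator, and if completing by link are already online; the protocol reports about 79% regular internet use in an earlier study. What remains is a difference in degree: intervention women get the booklet too, and have in addition the Website version of roughly 10 hours of content.
- **Exposure is limited.** Belief, self-efficacy and confidence items have little to look up. The 1-year measure is affected only if access persists, which is not stated. A reader might infer that the literacy result as a whole is compromised; the documents do not support that.
- **Size.** Doubling f = 0.12 to 0.24 SD would make a shift of 0.10 to 0.20 SD seem nearly as large as the design effect. That conversion belongs to two groups measured once. For the planned interaction over three measurements the comparator is 0.51 SD.
- **Motive.** Payment is for completion, and nothing ties it to scores.

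It can also be said that the access logs described under Intervention software platform let the problem be examined. They can show content use during the survey, but only for intervention women, and no analysis of them for this purpose is planned. None of this removes the gap: a self-completed knowledge test with no stated control on consulting the source.

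**Conclusion.** The concern holds in limited form. As written, the plan allows intervention women easier access to answers on the knowledge scales at the immediate post-test, and states no safeguard. On assumed shifts of 0.10 to 0.20 SD, the bias is about 20 to 40% of the design effect and moves the false-positive rate on a knowledge scale from 5% to about 8 to 18%. It is less if controls use the booklet.

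These figures rest on an assumed look-up share and gain, no look-up by controls, a shift at one time point only, N = 124 and r = 0.46. They show what could happen and do not estimate what will. This is a minor design point, worth settling because literacy is a primary outcome and the remedy is cheap.

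**What to change.** 1. State in Data collection whether Website content is available during the post-intervention survey. If it is, have the content management system pause the woman's access from opening the survey until she submits it.
2. Show the same short closed-book instruction in both arms, covering the Website, the booklet and web searches. A Website pause alone does not deal with the last two.
3. Record the mode of each survey: link alone, link with staff help, phone, or in person.
4. Report content access during the survey from the log, descriptively. Keep all randomised women in the primary analysis. Do not drop sessions with content hits: controls generate no such log, so the exclusion would act after randomisation and in one arm only.

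The cost is a software setting, one line of survey text and one recorded field. The system is already specified with PIN-protected access and use tracking. The drawback is a short pause in content access. For surveys already completed, item 4 is still possible if logs and surveys carry time stamps.

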described above, missing data due to either attrition or nonresponse will be fully recovered via multiple imputation in our intent-to-treat analysis, which will provide additional power and remove any confounding effect of missing data on our statistical power. For Aim 3, the key stakeholder interviews will occur with enough research participants to reach thematic saturation. Based on prior experience with key stakeholder interviews, we believe N~20 interviews will accomplish this goal,²⁷ but have resources to interview additional participants. Additionally, our COVID-19 module interview suggests N~30 interviews will accomplish the goal of thematic saturation.

Outcomes and instruments. Aim 1 feasibility outcomes include uptake of intervention components, barriers and facilitators of implementation, problems with delivery, and necessary modifications.⁴⁵ Pilot effectiveness outcomes will include an assessment of women's health literacy, operationalized as knowledge, beliefs, and self-efficacy for screening related to cervical, breast cancer, birth control, and STIs, post-intervention.^{4,26} Aim 2 RCT outcomes include women's health literacy, immediately post-intervention and 1-year post-intervention; and screening/ risk reduction for cervical, breast cancer, unintended pregnancy, and STIs at 1, 2, and 3-years post-intervention. Aim 3 outcomes include perception and uptake of intervention components.⁴⁵

Feasibility and perception of intervention outcomes are defined below and assessed through participant tracking and key stakeholder interviews with a subset of participants.:

- *Uptake of integrated, multimedia electronic women's health literacy intervention:* documentation of number of participants who responded to text messages; clicks on Website; real-time assessment of knowledge; time elapsed between text messages and Website clicks; number of outreach messages (through text, phone, or Facebook); Facebook posts/messages; chats with health educator; total minutes of contact through text, Web, chat, Facebook with each participant; attendance at community sessions
- *Barriers and facilitators of implementation:* problems described by participants in setting up text message platform, Website, closed Facebook group; factors that make set up of text message platform, Website, closed Facebook group ease of use; ease of Website components use (content modules, assessments)

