Validation strategies. Validation of data collected is an important aspect of rigorous outcomes assessment, especially since our primary outcomes of women's health literacy and screening/risk reduction are self-reported (see Table 5). In our original SHE study, we conducted a formalized evaluation of the accuracy of self-reported cancer screening with a subsample of women.⁵⁷ We found that 61% of Pap screening self-reports were accurate against medical record review. Importantly, Pap knowledge scores and semi-structured interview assessment of Pap events were statistically significantly associated with accurate Pap screening self-report. Thus, the conclusion of our validation study in SHE, was to analyze self-reported data for a weight for Pap knowledge scores and/or semi-structured interview assessment of Pap events (a total of four questions). For the purposes of the present study, for each outcome variable in Aim 1 (cervical, breast screening, birth control, and STI screening), we will weight self-reported data for knowledge scores in each of the domains of interest (cervix, breast, birth control, and STI knowledge).

To validate data collected in key stakeholder interviews, we will rely on reaching participant or thematic saturation.⁵⁸ We will interview a subsample of participants and will continue interviewing until we have reached thematic saturation, which will be determined by the study team and the PI, who has extensive expertise in qualitative methods in both research and implementation studies.

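### Weighting self-reported screening outcomes by domain knowledge does not correct reporting error, and with a post-randomisation score it could carry a knowledge effect into the arm comparison

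*Combined protocol and SAP*

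**What the plan says.** All references are to the combined protocol and SAP.

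- **Validation strategies** treats literacy and screening/risk reduction as self-reported primary outcomes. On the parent study it states: "We found that 61% of Pap screening self-reports were accurate against medical record review". Two markers were associated with an accurate report, and the parent study's conclusion was to use a "weight for Pap knowledge scores and/or semi-structured interview assessment of Pap events (a total of four questions". For the present trial the rule is introduced with "for each outcome variable in Aim 1 (cervical, breast screening, birth control, and STI screening" and continues "we will weight self-reported data for knowledge scores in each of the domains of interest (cervix, breast, birth control, and STI knowledge".
- **Standard of care discharge planning session (control arm)**: "In the Aim 1 pilot study, participants will only access the intervention arm content".
- **Outcomes and instruments**, for Aim 1: "Pilot effectiveness outcomes will include an assessment of women's health literacy, operationalized as knowledge, beliefs, and self-efficacy for screening". For Aim 2: "Aim 2 RCT outcomes include women's health literacy, immediately post-intervention and 1-year post-intervention", together with "screening/ risk reduction for cervical, breast cancer, unintended pregnancy, and STIs at 1, 2, and 3-years post-intervention".
- **Data analysis** describes repeated-measures mixed models for Aim 2 and mentions no weight. It does allow the matching domain knowledge score as a covariate in each screening/risk-reduction model, without saying when that score is measured.
- **Intervention arms and procedures** makes Knowledge the first day's content in the intervention arm. It also has a booklet with the intervention content mailed to all women.

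**The concern.** The weight is meant to answer a real weakness: about four in ten Pap self-reports disagreed with the medical record. A respondent's knowledge score does not tell the analyst whether her answer is wrong. Giving knowledgeable women more influence changes whose answers count and leaves the wrong answers in place. The supporting evidence concerns Pap self-report, yet the rule is extended to breast, birth control and STI outcomes.

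Knowledge is also something the intervention is designed to raise. If the score is taken after randomisation, the weight becomes a consequence of arm, and a gain in knowledge could appear as a gain in screening when behaviour has not changed. Because the form and timing of the weight are open, they could be settled after results are known.

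**Working it through.** **1. Which aim the rule can apply to.** Aim 1 has one arm, and its effectiveness outcomes are literacy only. The cervical, breast, birth control and STI screening outcomes named in the rule appear as outcomes only under Aim 2, at years 1, 2 and 3. Read literally, the rule governs outcomes that Aim 1 does not have. The sensible reading is that it governs the trial, but the text does not say so.

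**2. Inputs.** From the documents: accuracy 0.61 (Validation strategies), and 59/261 = 22.6% with no Pap test in three years (Table 1), so about 77% reporting one. The plan gives no figure for the effect of the weight, so there is none to reproduce, and the sample size is not affected. Everything else below is an assumption. Knowledge is scored 0 to 1.

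**3. Does weighting correct misreporting?** Let p be the true rate and a the accuracy, with errors in both directions. The reported rate is R = a·p + (1 − a)(1 − p). Assume p = 0.60, control knowledge K with mean 0.50 and SD 0.15, and accuracy rising with knowledge as a = 0.61 + 0.6(K − 0.50).
- Unweighted: 0.61 × 0.60 + 0.39 × 0.40 = 0.522.
- Weighted by K: the weighted mean of K is 0.50 + 0.15²/0.50 = 0.545, so a = 0.61 + 0.6 × 0.045 = 0.637. Then R = 0.637 × 0.60 + 0.363 × 0.40 = 0.527.
- Over-reports only, with p = 0.40: R = p + (1 − a) = 0.79 unweighted, and 0.40 + 0.363 = 0.763 weighted, against a true 0.40.
- For contrast, a correction that uses sensitivity and specificity (both 0.61 in the first case) recovers the truth: (0.522 + 0.61 − 1)/(0.61 + 0.61 − 1) = 0.132/0.22 = 0.60.

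Between arms, with no behavioural effect and a knowledge gain of 0.10, better reporting alone gives 0.06 × (2 × 0.60 − 1) = 0.012 unweighted. Weighted, accuracy in the intervention arm is 0.61 + 0.6 × (0.60 + 0.0225/0.60 − 0.50) = 0.6925, and (0.6925 − 0.637) × 0.20 = 0.011. With over-reports only (p = 0.60), simulation gives −0.040 unweighted and −0.043 weighted. Weighting barely changes either difference.

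**4. Post-randomisation score multiplied into the outcome.** With no behavioural effect, the spurious difference is the reported rate times the knowledge gain:
- gain 0.05: 0.77 × 0.05 = 3.9 points
- gain 0.10: 0.77 × 0.10 = 7.7 points
- gain 0.15: 0.77 × 0.15 = 11.6 points

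The low end is the more plausible. The Power section's average literacy effect of f = 0.13, read as a two-group Cohen's f, is d = 0.26. With SD 0.15 that is a gain of 0.039, or 0.77 × 0.039 = 3.0 points. In a simulation with 100 per arm, a true rate of 0.60, control mean 0.50 and SD 0.15, a nominal 5% test rejects about 12%, 30% and 75% of the time for gains of 0.05, 0.10 and 0.20. Unweighted reports stay at about 5%.

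**5. Post-randomisation score as a case weight.** The arm estimate is Σ(wY)/Σw. If behaviour is unrelated to knowledge and there is no misreporting, the difference is zero. Otherwise, assume a share of women engage, engagers screen more in both arms, and engagers gain knowledge. The control estimate is the plain mean when controls gain nothing.

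| Engagers; screening rates; weight | Intervention | Control, no gain | Difference | Difference if control engagers gain half as much |
|---|---|---|---|---|
| 50%; 85% vs 70%; 0.6 to 0.8 | 0.55/0.70 = 78.6% | 77.5% | +1.1 | 78.6 − 0.5075/0.65 (78.1) = +0.5 |
| 50%; 90% vs 60%; 0.5 to 0.8 | 0.51/0.65 = 78.5% | 75.0% | +3.5 | 78.5 − 0.4425/0.575 (77.0) = +1.5 |
| 40%; 90% vs 60%; 0.4 to 0.8 | 0.432/0.56 = 77.1% | 72.0% | +5.1 | 77.1 − 0.36/0.48 (75.0) = +2.1 |

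The sign can reverse. In the first row, if the lower-screening half gains the knowledge instead, the intervention estimate is (0.5 × 0.6 × 0.85 + 0.5 × 0.8 × 0.70)/0.70 = 76.4%, a difference of −1.1.

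**6. Baseline score.** Randomisation balances it in expectation, so steps 4 and 5 give no systematic arm difference. Step 3 still applies.

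**The case against.** The strongest reply is that the text never commits to a weight that differs by arm. It names a single-arm aim and gives no time point. A reader might infer that the weights differ by arm by design. That needs both application to Aim 2, which is likely but unstated, and a post-randomisation score, which is not stated at all. This part of the reply stands, and the arm-related bias must remain conditional.

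Second, Data analysis contains no weight but uses the same domain scores as covariates, so the loose wording may mean covariate adjustment. That is possible. A spurious benefit through a weight would then not follow, but adjusting for knowledge measured after randomisation would remove part of any effect that works through knowledge. The two sections would still need to be reconciled.

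Third, the bias may be small. Multiplying a yes/no outcome by a score is not the most natural reading of a weight, and all women receive the booklet, so controls may learn too. With Table 4's 170 women at year 1, about 85 per arm, the standard error of a difference near 75% is √(2 × 0.75 × 0.25/85) = 6.6 points, larger than any case-weight figure above. This stands as to size. It does not make the weight useful.

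Fourth, unweighted self-report also leaves reporting error in place. That is true, and it is why a separate sensitivity analysis is needed. The parent study's four interview questions are not a ready substitute. They too were only associated with accuracy, and they come from a semi-structured interview, whereas Data collection makes audio computer-assisted self-interview the default.

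A reader might also infer that no concurrent knowledge score exists at years 2 and 3, since Overview of study and Outcomes and instruments schedule literacy only to year 1. Table 3 lists literacy assessment at years 1, 2 and 3 as well. The schedules conflict and should be reconciled, but absence of the score cannot be concluded.

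**Conclusion.** The point holds in part: should-fix, with medium confidence. Two faults hold however the rule is implemented as a weight. It does not correct wrong answers, so the problem behind the 61% accuracy remains, and its support is limited to Pap self-report. A third is conditional: with a post-randomisation score in Aim 2, a knowledge effect can leak into the screening comparison. The sizes in steps 4 and 5 rest on assumed knowledge gains, engagement shares and screening rates. They show what the undefined rule permits and are not estimates of bias in this trial.

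**What to change.** - Correct the aim label in Validation strategies.
- Make unweighted self-report the primary screening/risk-reduction outcome in both arms.
- Keep post-randomisation knowledge out of the primary screening analysis, both as a weight (Validation strategies) and as a covariate (Data analysis).
- If knowledge weighting is kept, define its form in advance and confine it to a prespecified sensitivity analysis for Pap, using the baseline score.
- Examine misreporting in a sensitivity analysis over assumed sensitivity and specificity, allowed to differ by arm. The documents give only overall accuracy, so the range must be stated as an assumption.
- Reconcile the literacy assessment schedule between Table 3 and the sections that stop at year 1.

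The cost is a change of wording, a little more analysis work, and loss of comparability with any weighted result from the parent study. No new data and no change in sample size are needed.
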